12.3 MAJOR ADVERSE EVENT

An event occurring during the trial that meets one of the following criteria:

- *All-Cause Mortality*:
- Death is defined as any death occurring during the trial period, regardless of cause.
 - O Aneurysm-related death: is defined as any death occurring within 30-days from the date of the index procedure, regardless of cause, and death due to aneurysm rupture or death within 30-days of any secondary procedure intended to treat the aneurysm.
 - o Cardiac-related death: is defined as death due to arrhythmia, heart failure (including cardiogenic shock), or myocardial infarction
 - o *Pulmonary-related death:* is defined as death due to due to pulmonary edema, respiratory failure, or pulmonary embolism
 - Vascular-related death: is defined as death due to stroke, cerebral hemorrhage, or other clear vascular event that is not categorized as cardiac-related or pulmonary-related or aneurysm-related.
 - o *Other:* is to be used to identify a death due to any event that cannot be clearly categorized as above, but where some information is available.
 - o *Unknown*: is to be used to identify a death where no information is available.
- *Bowel Ischemia:* the lack of adequate blood flow to the intestines that requires intensification of medical therapy or surgical/endovascular intervention.

- Myocardial Infarction: increase of one or more cardiac biomarkers (preferably troponin) with at least one value above the 99th percentile of the upper reference limit (URL) together with evidence of myocardial ischemia with at least one of the following: myocardial ischemia; ECG changes indicative to new ischemia (new ST-T changes or left bundle branch block (LBBB)); development of pathological Q-waves in the ECG; imaging evidence of new loss of viable myocardium or new regional wall motion abnormality.
- Paraplegia: paralysis of the lower extremities inclusive of the lower trunk;
- Renal Failure permanent dialysis dependence or kidney transplant
- Respiratory Failure: respiratory failure requiring ventilator support beyond 24 hours post-procedure
- *Stroke:* a sudden development of neurological deficit due to vascular lesions of the brain such as hemorrhage, embolism, or thrombosis that persists for >24 hours;
- *Index Procedural Blood Loss* >1,000mL: estimated blood loss during the index procedure ≥1,000mL.

12.4 OTHER DEFINITIONS

- Luminal Thrombus Requiring Intervention: any endovascular surgical intervention after completion of the device implantation for resolution of endograft thrombosis.
- *Distal Ischemia*: new onset of compromised peripheral blood flow resulting in femoral or peripheral arterial occlusion or stenosis (attributable to the index procedure or to the endograft and not related to natural progression of atherosclerotic disease) causing a threat to the viability of the limb and requiring surgical or percutaneous intervention; or stent graft occlusion requiring any intervention.
- Occlusion requiring intervention: intervention for stent graft occlusion
- Secondary Endovascular Procedure: any non-diagnostic intervention after the index procedure intended to correct or repair an Endoleak, device stenosis or occlusion, migration, aneurysm sac expansion and/or a device defect (including infection);
- Successful Implantation: Successful delivery and deployment of the device.
- *Modified Intention-to-Treat:* analysis of the results of implanted patients is based on the initial treatment assignment and not on the treatment eventually received.

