Secondary Endpoints	 MAEs at 30-Days, 12 Months and Annually ARC Post 12 Months up to Five Years Aneurysm Related Mortality Endoleaks Classified by Type AAA Related Secondary Procedures up to Five Years Device integrity Any adjunctive procedures necessitated during the implant procedure 					
Additional Evaluations	 Total Endovascular time; from catheter introduction to catheter removal Anaesthesia Time Fluoroscopy Time Contrast Volume used Total Procedure Time; from cut-down to closure Time in ICU Total Radiation Exposure Additional Imaging 					

Statistical Considerations

The primary endpoint will be evaluated in both the AFX and proximally fixated device groups. The relative performance of the two groups will be evaluated through one-sided tests for non-inferiority and superiority. Combining the superiority and non-inferiority trials into a single closed testing procedure allows for maintenance of a controlled Type 1 error rate. An 8% margin will be used for the non-inferiority test. If the non-inferiority null hypothesis is rejected, the null hypothesis for superiority will be investigated.

Hypotheses for Non-Inferiority:

Null Hypothesis: $H1_0$: $\mu_A - \mu_B \le -8\%$ (AFX is inferior with respect to the

primary endpoint)

Alternative: $H1_1: \mu_A - \mu_B > -8\%$ (Statistical evidence of non-

inferiority)

Hypotheses for Superiority:

Null Hypothesis: $H2_0$: $\mu_A - \mu_B \le 0$ (The two device groups have equal effect)

Alternative: $H2_1$: $\mu_A - \mu_B > 0$ (Statistical evidence of superiority)

The original trial size was selected to provide 80% power for the superiority test. The original sample size required, for non-inferiority testing, is relatively smaller; thus, the power of the non-inferiority test approaches 100% with the revised sample size.

Suggested Schedule of Tests

Patient eligibility will be assessed by the Investigator per institutional standard of care pre-procedural imaging. Blood work and physical exam will also be collected as per routine schedule at each institution.

Following Institutional Review board approval and patient written informed consent, the patient will be screened for eligibility. Subjects will be followed procedurally and to hospital discharge and per institutional standard of care thereafter through to 5 years (total follow-up commitment).

Table 1 outlines a typical site follow-up schedule which will be altered to meet standard of care at individual sites.

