4.5 TRIAL DESIGN

The LEOPARD trial is a prospective, randomized, multi-center trial, intended to evaluate the outcomes of contemporary EVAR (Endovascular Aneurysm Repair) in a real-world population. The trial is designed to compare the anatomically stabilized AFX Endograft System to a reference group of proximally fixated EVAR devices. Patients will be randomized between the two groups.

Randomization will be 1:1. Each Investigator will select one comparator device of their choice before enrolling the first patient and this device will serve as the comparator device for that Investigator throughout the course of enrollment. The trial will sequentially evaluate non-inferiority and superiority hypotheses.

[figure not shown]

Figure 1: Randomization Scheme

All subjects undergoing EVAR with either the AFX System or the reference group of other EVAR devices will be followed procedurally to discharge, at 1, 6 (standard of care follow-up, no specific trial visit is required), 12 months and annually through to 5 years (total follow-up commitment).

After this protocol and the patient Informed Consent Form (ICF) are reviewed and approved by the local Institutional Review Board (IRB), potential subjects having infrarenal AAA will be offered participation in the trial. This will be accomplished through the patient's reading of the informed consent form and discussion of the trial with the patient by the Investigator and site personnel. Agreement to participate and to attend all protocol required follow-up visits will be documented with the patient's signature on the informed consent form.

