7 ADDITIONAL EVALUATIONS

Additional evaluations include the following procedural and in-hospital evaluations:

1. Procedural Technical Failure

- 2. Total Endovascular time; from catheter introduction to catheter removal
- 3. Anesthesia Time
- 4. Fluoroscopy Time
- 5. Contrast Volume used
- 6. Total Procedure Time; from cut-down to closure
- 7. Time in ICU
- 8. Total Radiation Exposure

The procedural technical failure is defined as a failure of the AFX® System or comparator devices to be delivered and deployed, such that the procedure is not completed, or the device failure results in a serious complication, or residual Type I and Type III Endoleaks which occur and cannot be resolved during the index procedure.

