10.2 STATISTICAL METHODS

All non-imaging-driven variables in the composite endpoint will be evaluated to 1 year (day 365 post-implant), whereas imaging-driven variables will be evaluated to a 1-year window (day 365 +/- 60 days). The day of implantation will be set as day 0. Early events are defined as those occurring from the date of the procedure up to 30 calendar days post-operatively. Late events are defined as those occurring from after 30 calendar days post-operatively (from day 31 forward).

The null hypotheses for both non-inferiority and superiority will be evaluated with one-sided alpha levels of 0.05.

If the non-inferiority null hypothesis is rejected, the null hypothesis for superiority will be investigated.

Hypotheses for Non-Inferiority:

Null Hypothesis:

 $H1_0$: $\mu_A - \mu_B \le -8\%$ (AFX is inferior with respect to the primary

endpoint)

Alternative: $H1_1$: $\mu_A - \mu_B > -8\%$ (Statistical evidence of non-inferiority)

Hypotheses for Superiority:

Null Hypothesis: $H2_0: \mu_A - \mu_B \le 0$ (The two device groups have equal effect)

Alternative: $H2_1$: $\mu_A - \mu_B > 0$ (Statistical evidence of superiority)

Data for the primary endpoint will be presented as point estimates for both the treatment (AFX device) and control (proximally fixated devices), along with a 95% confidence interval for the difference. The lower bound of a one sided 95% confidence interval is used to evaluate the non-inferiority and superiority null hypotheses.

Quantitative parameters will be described using the following summary descriptive statistics: number of non-missing values, mean, standard deviation, median, first and third quartiles, and minimum and maximum values.

Qualitative parameters will be described overall using frequencies and percentages. Percentages will be calculated on the number of non-missing observations. In all cases, the number of missing values will be specified.

Kaplan-Meier estimates will be generated for the composite endpoint components across the duration of the trial.

Sample Size Determination:

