Given an alpha error rate of 0.05, a desired power of 90%, and assuming a success rate (in terms of the primary endpoint) of 86% for AFX with an 8% advantage over the control group, the sample size required to demonstrate non-inferiority is 154 subjects in total. In order to have enough power to evaluate all hypotheses the sample size for this trial was driven by the evaluation of superiority. In this case, an alpha error rate of 0.05, power of 80%, success rate of 86% for AFX, and a relative 8% advantage in AFX's favor requires 566 patients. A 7% advantage in AFX's favor requires 724 patients. An approximate dropout rate of 10%/1-year indicates 804 patients should be enrolled to provide 724 patients at 1 year. The original protocol thus called for enrollment of up to 800 subjects. The enrollment was completed at 455 subjects after an unplanned analysis supported that the superiority evaluation was futile. With a total of 455 subjects enrolled, 410 are assumed to reach the 1-year endpoint after 10% dropout. This sample size results in 99% power for the non-inferiority test under original assumptions, and thus the trial is considered adequately powered for evaluating non-inferiority. The sample size has been determined with PASS version 12.0.2.

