12 DEFINITIONS

12.1 DEFINITIONS ASSOCIATED WITH THE COMPOSITE PRIMARY ENDPOINT ARC

The primary trial endpoint is an assessment at one year, where survival is in the absence of Aneurysm Related Complications (ARC). ARC is a composite of the most relevant EVAR related outcomes and include:

- *Aneurysm Rupture*: bleeding or leaking of blood from the aneurysm subsequent to the index procedure.
- Conversion to Open Surgical Repair (OSR): open surgical repair of the abdominal aortic aneurysm due to unsuccessful delivery or deployment of the stent graft, due to complications or other clinical situations that precluded successful endovascular treatment, or at any time following initial successful endovascular treatment for any reason. Excludes post-mortem explant of the trial device.
- Endoleaks: clear evidence of contrast within the aneurysm sac
 - **Endoleak Type Ia** Contrast material in the aneurysm sac adjacent to the proximal seal zone and/or between the endograft and the inner wall of the proximal attachment site.
 - **Endoleak Type Ib** Contrast material in the aneurysm sac adjacent to the distal seal zone and/or between the endograft and the inner wall of the distal attachment site.
 - **Endoleak Type II** Contrast material along the posterior sac wall with visualization of lumbar artery or the inferior mesenteric artery

LEOPARD AAA US Post-Market Trial

- Endoleak Type IIIa Component disconnect
- Endoleak Type IIIb Mid-graft hole
- *Migration* (≥10mm): stent distal movement ≥10mm from the original implant location relative to the center of the distal renal artery; as compared to the 1-month CT scan location.
- Aneurysm Sac Enlargement: aneurysm sac diameter increase of ≥5mm in late followup as compared to 1-month CT scan location.
- *Endograft Limb Occlusions*: defined as total obstruction of blood within the lumen of a device limb irrespective of whether a secondary intervention is necessary.
- *Endograft Stenosis:* defined as a reduction in lumen >50% by, for example, thrombus, intimal hyperplasia, or endograft kink/twist.

Elaboration of the above definitions can be found in the Adjudication Charter.

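### The −8% non-inferiority test has no supporting analysis for patients whose assigned device was replaced by another endograft at the index procedure

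*Combined protocol and SAP*

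**What the plan says.** **Who is analysed, and in which arm.** Section 10.1 bases the primary analysis on mITT: randomized subjects who went on to have EVAR, with no mention of which device. Section 12.4 refers to implanted patients and says the analysis "is based on the initial treatment assignment and not on the treatment eventually received". Sections 5.4 and 5.6 place enrollment earlier, when the delivery system or device enters the patient.

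**What counts as an ARC event.**
- Conversion to open repair is a component. Section 12.1 defines it to include "open surgical repair of the abdominal aortic aneurysm due to unsuccessful delivery or deployment of the stent graft".
- Reinterventions for device- or aneurysm-related complications are listed in 6.1 but not defined in 12.1.
- The nearest defined term, Secondary Endovascular Procedure in 12.4, covers "any non-diagnostic intervention after the index procedure intended to correct or repair an Endoleak" and similar problems, so it starts after the index procedure.
- No component names failure of the assigned device or completion of the case with another endograft.

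**What is only reported separately.** Technical failure is an additional evaluation in section 7. Its first limb is a "failure of the AFX® System or comparator devices to be delivered and deployed, such that the procedure is not completed". Adjunctive procedures during implantation are a secondary endpoint (6.2).

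**The test.** Section 10.2 states: "The null hypotheses for both non-inferiority and superiority will be evaluated with one-sided alpha levels of 0.05". The Synopsis adds: "An 8% margin will be used for the non-inferiority test". Only AFX is tested for non-inferiority. No as-treated, per-protocol or device-switch analysis is described.

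**The concern.** Take a patient assigned to AFX whose delivery system is inserted but whose graft cannot be deployed, and whose case is completed with a comparator endograft. The patient has undergone EVAR and so belongs to the mITT set, in the AFX arm. If the comparator graft then performs well for a year, no listed ARC event has clearly occurred. The device that failed is credited with the result of the device it is being compared with. The same happens in reverse for a comparator patient rescued with AFX.

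Such cases are feasible, because section 5 requires every investigator to be certified on both AFX and the chosen comparator. Section 10.1 itself warns that groups which become more alike bias the result towards non-inferiority. It says so about subjects who are never implanted, but device switching works the same way.

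The stakes rose with Revision 02. Superiority was judged futile after an unplanned analysis and the sample size was re-justified for non-inferiority. That conclusion now rests on one analysis, with nothing beside it to show whether rescue contributed.

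**Working it through.** **Inputs from the documents.** One-sided alpha 0.05 and margin 8 points (10.2, Synopsis). Planning rates come from "assuming a success rate (in terms of the primary endpoint) of 86% for AFX with an 8% advantage over the control group", that is 86% and 78%. Allocation: "Randomization will be 1:1". There are 455 enrolled with 10% dropout; 455 × 0.9 = 409.5, stated as 410, or 205 per arm.

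**Formula.** With A for AFX and B for control:

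P(declare non-inferiority) = Φ[(pA − pB + 0.08)/SE − 1.645], SE = √[pA(1 − pA)/205 + pB(1 − pB)/205]

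**The plan's own figure.** pA = 0.86 and pB = 0.78 give SE = 0.0377. Then 0.16/0.0377 = 4.24, and Φ(4.24 − 1.645) = 99.5%. The stated 99% power reproduces.

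**Effect on false non-inferiority.** Assumptions, not in the documents:
- The true rates are 78% AFX and 86% control when rescued cases count as failures, so AFX sits exactly at the margin.
- b is the net excess of rescued cases in AFX over control.
- s, the share of rescued patients otherwise free of ARC at one year, is 0.80 to 0.86.

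The rate the analysis would see for AFX is 0.78 + b × s.

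| b (points) | Difference seen (points) | P(declare non-inferiority) |
|---|---|---|
| 0 | −8.0 | 5.0% |
| 1 | −7.2 to −7.1 | 7.6–7.9% |
| 2 | −6.4 to −6.3 | 11.2–11.9% |
| 3 | −5.6 to −5.4 | 16.0–17.3% |
| 5 | −4.0 to −3.7 | 29.5–32.6% |

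A second parameterisation sets x as the net share rescued and otherwise ARC-free, so no s is needed. For x = 1, 2, 3 and 5 points it gives 7.9, 12.0, 17.4 and 32.6% with control at 78% and AFX at 70%. With control at 86% and AFX at 78% it gives 8.4, 13.5, 20.5 and 40.3%.

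**Effect on power if those x points are scored as failures.** Here pA is reduced by x:

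| x (points) | About n of 205 | 86% vs 78% | Both 78% | Both 86% |
|---|---|---|---|---|
| 0 | 0 | 99.5% | 62% | 75% |
| 1 | 2 | 98.9% | 52% | 64% |
| 2 | 4 | 97.6% | 42% | 52% |
| 3 | 6 | 95.4% | 33% | 40% |
| 5 | 10 | 86.8% | 17% | 20% |

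**How few cases could matter.** One reclassified subject moves the difference by 1/205 = 0.49 points. With both arms near 78%, the half-width 1.645 × √(2 × 0.78 × 0.22/205) is 6.7 points, so non-inferiority needs an observed difference above about −1.3. Near 86% the half-width is 5.6 points and the threshold about −2.4. A few net cases could decide a close result.

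**The case against.** **Scoring as success is not a stated rule.** A reader might infer that the protocol counts a rescued patient as ARC-free. It does not say so. Reintervention is undefined, and the limit to procedures after the index operation belongs to a different term. Section 12.1 refers to an Adjudication Charter for elaboration, and 10.2.3 lets the adjudicator overrule site and core lab. Neither the Charter nor separate SAP text was available for this review. The rescued patient must also avoid every other ARC event for a year. This stands, and is why the verdict says probably.

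**The contrast with open conversion is not secure.** A reader might infer that the same failure treated by open repair always counts against the arm. Section 12.1 makes it an ARC event, but 10.1 requires that EVAR was undergone and 12.4 speaks of implanted patients. A conversion with nothing implanted could fall out of the analysis set. This also stands. It adds a second ambiguity about failed devices and does not remove the first.

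**The direction is not automatic.** The scoring applies to both arms and only AFX is tested for non-inferiority. Excess rescue among comparators would make non-inferiority harder to show. Nothing in the documents suggests an AFX excess.

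**The size is hypothetical.** The inflated error rates assume a deficit at the margin, the reverse of the planning rates. That is correct, although a false non-inferiority rate has to be evaluated there, and the planning advantage is doubtful once superiority was judged futile.

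**Analysis by assignment is sound.** It is ordinary intention-to-treat practice, and outcome under the assigned strategy is a legitimate estimand. Rescoring the primary endpoint now, after enrollment closed, an unplanned analysis was done and ARC was analysed, would be a data-informed change. Both points are accepted; neither argues against supportive analyses.

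**Conclusion.** The concern holds as a missing safeguard. The non-inferiority conclusion rests only on mITT by assigned arm, no ARC component clearly captures an index-procedure switch to another endograft, and no supporting analysis would reveal its influence. A net AFX excess of such rescues would probably be scored as AFX success and bias the −8% test towards non-inferiority.

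The size depends on a rescue rate the documents do not give. With the truth at the margin, 205 per arm and 80–86% of rescued patients otherwise ARC-free, net excesses of 1, 2, 3 or 5 points turn 5% into about 8%, 12%, 16–17% or 30–33%. At the planning rates the issue is minor: power stays near 95% with a 3-point excess counted as failures. It matters when true rates are equal or near the margin.

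The documents do not support saying that non-inferiority has been, or will be, met through rescue with the rival device.

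**What to change.** Keep the primary endpoint and the mITT analysis. Add to section 10.2:

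1. A supportive analysis of the −8% test that scores as failures, for the assigned arm, all subjects whose assigned delivery system was inserted but whose procedure was completed with a non-assigned endograft, or who had unresolved technical failure.
2. An as-treated analysis of the same test.
3. Counts of device switches and technical failures by arm, with the non-inferiority conclusion reported beside these results.

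In 12.1, define reintervention and its time origin, stating whether an index-procedure switch is included. If the Adjudication Charter already settles this, a cross-reference is enough. Reconcile 5.4, 10.1, 12.1 and 12.4 so that a failed deployment converted to open repair without an implant stays in the analysis as the ARC event that 12.1 describes.

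**Cost.** Some wording and one or two extra analyses, labelled as added after the unplanned analysis. No new visits are needed. The sponsor should confirm that the eCRF identifies the device actually implanted: the first limb of the section 7 definition requires an uncompleted procedure, so a completed rescue may not be recorded as a technical failure. The supportive result may be less favourable than the primary one.

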13 RESPONSIBILITIES

13.1 SPONSOR RESPONSIBILITIES

This trial is conducted under the responsibility of Endologix. Only Endologix staff and designees approved by Endologix will participate in this trial. Endologix is responsible as the Sponsor to ensure:

- Proper site and Investigator selection
- Availability of signed Investigator agreements prior to trial initiation
- Availability of regulatory and IRB approval prior to the initiation of the trial at any site

- Management and monitoring of the trial with special attention to verification of all clinical requirements, adherence to protocol, good clinical practices and compliance with applicable government and institutional regulations
- Furthermore, the sponsor is responsible for ensuring proper regulatory approvals are obtained, and reporting to regulatory authorities per applicable regulations
- Sites are supported and adequately trained on the device

